## 5.2.7 Product accountability

A pharmacy in each region will act as the study central pharmacy and coordinate the storage, distribution and maintain accountability records of the BCG vaccine and placebo supply in that region as appropriate. The RCH pharmacy will act as the study central pharmacy for Australia. The UMC Utrecht pharmacy will be the study central pharmacy in mainland Europe. A UK based pharmacy will act as the central study pharmacy should any UK sites be included in the trial. The LAC/UFMS will act as the central pharmacy in Mato Grosso do Sul, Brazil and a central pharmacy in Rio De Janeiro and Manus will be managed through the collaborating institution. Trial accountability of IP including documentation of storage, dispensation and destruction (if required) will be maintained in the pharmacy files at each region/site as appropriate. A pharmacy summary/manual will outline the specific processes for each region in line with local processes and regulations.

Any reason for departure from the expected dispensing regimen will be recorded. At the end of the trial, there will be final reconciliation of trial drug received, dispensed, used and returned. Any discrepancies will be investigated, resolved and documented by the study team.

#### 5.2.8 Excluded medications and treatments

BCG vaccination may be given on the same day of any inactivated or live vaccines. If not given on the same day a period of not less than 4 weeks must pass before giving another live vaccine (although there is no real data supporting this precaution). There must be an interval of at least 3 months before a vaccination in the same arm can take place. Inactivated vaccine (such as the diphtheria-tetanus-pertussis vaccine) can be given in the other arm at any time before, during, or after BCG vaccination if needed.

Participants should not take part in any other COVID-19 preventative intervention clinical trials during the 6 month follow-up period.

## 5.2.9 Discontinuation from trial intervention

The trial intervention is a once-off vaccination. Due to this there is no possibility to 'discontinue the trial intervention'. If a participant changes their mind between randomisation and vaccination, deciding that they do not want to have the vaccination (but are happy to continue in the study for the follow-up period) they will be included in the analysis as intention to treat.

## 6 RANDOMISATION AND BLINDING

Once consent has been obtained, and following baseline assessment, eligible participants will be recruited and randomised on the day of the enrolment via REDCap. Randomisation will be to intervention or placebo group with an allocation ratio of 1:1, using a web-based randomisation procedure. The randomisation schedule and web-based service will be provided by an independent statistician from the Clinical Epidemiology and Biostatistics Unit (CEBU) at the Murdoch Children's Research Institute. Randomisation will be in randomly permuted blocks of variable length (2, 4, or 6). Randomisation will be stratified by stage of the study (prior to or post the addition of the placebo vaccination), study site, by age (<40 years; 40 to 59 years; >=60 years) and by presence of comorbidity (any of diabetes, chronic respiratory disease, cardiac condition, hypertension). Stratification by age is necessary for data analysis because

[figure not shown]
older ages are associated with a greater likelihood of developing severe COVID-19. Likewise, presence of comorbidity is associated with a greater risk of developing severe COVID-19. Each study site will have their own randomisation list stratified by study stage (where relevant), age and presence of comorbidity.

## 6.1 Concealment mechanism

The control group will receive a placebo of 0.9% NaCl. Most people vaccinated with the BCG vaccine develop a papule/blister at the injection site around two-weeks after vaccination. Due to this, even using a placebo, it is not completely possible to blind participants to their treatment group allocation. The outcomes (symptomatic and severe COVID-19 or admission to hospital for COVID-19) are objective measures, it is however still plausible that participant's suspicion of their group allocation might bias the study results. This risk will be mitigated by using a placebo where an element of doubt over treatment allocation may persist even in the absence of scar formation. Members of the study team, except immunisers, will be blinded to the group allocation (by the removal of this variable and all other variables related to BCG from the dataset) until the formal detailed statistical analysis plan is confirmed and signed by all investigators and all data cleaning/preparation is complete.

#### 7 TRIAL VISITS AND PROCEDURES

## 7.1 TRIAL TIMELINE

Study Name: BCG vaccination to Reduce the impact of COVID-19 in healthcare workers (BRACE) trial

RCH HREC number: 62586

Version & date: version 12.0 dated 17May2022

## 7.2 Schedule of assessments

	TRIAL PERIOD									
	Pre-study	Inclusion & randomisation	Post-randomisation							
TIME POINT	t-1	to	t 1-12	t 13	t 14-25	t 26	t 27-38	t39	t40-51	t 52
RECRUITMENT:										
Eligibility screen	Χ									
Informed consent	Χ									
Contact details	Χ									
Allocation to intervention		Χ								
INTERVENTIONS:										
BCG vaccine		X (BCG group)								
Saline injection		X (Placebo group)								
ASSESSMENTS:										
Baseline questionnaire	Χ	X								
Weekly survey			Χ	Χ	Χ	Χ	X	Χ	Χ	Χ
Instruction for swab testing (if indicated by weekly survey)			(X)	(X)	(X)	(X)	(X)	(X)	(X)	(X)
3-month survey				Χ						
6-month survey						Χ				
9-month survey								Χ		
12-month survey										Х
Clinical advice on injection site *			Χ	Х						
Blood collection**		X		Х		X		X#		X#
Baseline SARS-CoV-2 Test ***		X								

T=week (e.g. t1=first week). A 42day window period is accepted for the periodic survey and the blood collection timepoints

# Sub-set of participants

#### 7.3 Description of procedures

The procedures related to recruitment, consent, eligibility confirmation, randomisation and intervention are described in sections 4 and 5 of this protocol. The procedure for blood collection is described in the relevant SOP. Capture of applicable adverse events is described in section 8.

In Brazil only, a baseline respiratory swab will be collected as outlined in appendix 4.

After randomisation there are two key aspects of the 1-year follow-up period; questionnaires and sample collections for SARS-CoV-2 identification (respiratory swabs or blood samples). Participants will be asked to complete a questionnaire using the smartphone application (app) designed for the trial, electronic messages or via phone calls to report symptoms, access SARS-CoV-2 testing through the public health system and if needed self-collect a respiratory swab each time they have a febrile illness or a respiratory symptom. Where app is utilised, participants will be trained on how to use the app on day of enrolment.

st In indicated Infectious Diseases clinician, or state-based organisation, as appropriate

\*\* Optional consent for additional biological sample including blood sample when illness reported

\*\*\* Brazil only as outlined in Appendix 4

#### Questionnaires

#### Baseline

- Comorbidities: diabetes, cardiovascular disease, chronic respiratory disease, hypertension
- Risk factors: smoking, body mass index (calculated with weight and height)
- BCG/TB history: Prior BCG vaccination, ever positive TST
- Influenza immunisation: date of last influenza vaccine (if within influenza season)
- Exposure (presence of COVID-19 cases at workplace, average days working in hospital or other healthcare settings as appropriate)
- Other: Recurrent herpes infection (such as cold sores)

Regular (generally weekly) questionnaires on smartphone app, via phone call or via electronic messages

 Any symptoms of COVID-19: fever or at least one sign or symptom of respiratory disease such as sore throat, cough, shortness of breath, respiratory distress/failure (y/n)

For each episode of illness (via smartphone app, via phone call or via electronic messages)

- Which symptoms of COVID-19: fever, cough, shortness of breath and/or difficulty breathing, runny/blocked nose, sore throat, fatigue, muscle and/or joint ache, headache, nausea, vomiting and/or diarrhoea, loss of taste and smell
- Has a COVID-19 swab been taken? (if so what was the result)
- Date of/days since onset and cessation of symptoms
- Days absent from work (total number and number due to illness)
- ED presentations
- Hospital admission (oxygen, ICU admission, mechanical ventilation)
- Known test results
- If a swab has been taken for clinical purposes, who ordered it
- Impact on daily activities
- Days in bed
- Chest x-ray results

For local reaction to injection: the Vaccine Diary (daily diary for the two weeks following injection)

 Questionnaire collecting common reactions to the injection, including photograph of injection site

Periodic questionnaires (once every 3 months)

- Exposure (presence of COVID-19 cases at workplace, average days working in hospital or other healthcare settings as appropriate)
- Cold sore recurrence
- Request for participants to confirm the main episodes of illness experienced in the prior 3 months.
- Screening, exposure or treatment of TB

- Detail on other vaccinations
- Hospitalisation (any)
- Information regarding participation in any other COVID-19 preventative intervention clinical trials
- Injection site evolution and side effects (photo of injection site)
- Treatment that could influence COVID-19 outcome

## Additional questions for 3rd month questionnaire only:

- Record any non-serious adverse event of interest, including Injection site evolution and side effects (photo of injection site), with onset between randomisation and 3 months post randomisation
- If relevant: Influenza vaccine side effects
- Record any serious adverse event with onset between randomisation and 3 months post randomisation

#### Swabs

 Where a participant has had a swab sample assessed outside the indication of the study (e.g. with non-respiratory symptoms or asymptomatic) results will be collected via self-report. All test results will also be obtained, where possible, from centralised SARS-CoV-2 testing government database.

Where a participant has symptoms of febrile or respiratory illness (cough, sore throat, shortness of breath) and a swab sample for SARS-CoV-2 is not collected through standard pathways (for example due to swab shortage, or government decision to restrict screening to high-risk patients), a sample collection study visit may be done. A respiratory swab/s may be collected from the participant at home and linked with the relevant public health testing and reporting systems. If respiratory swab/s are done by participant self-collection (e.g. nasal/throat swabs) they will receive full instructions on how to take the samples, when to take them and how to correctly store them until a member of the research team collects them.

#### **Blood samples**

- At randomisation, a blood sample will be taken for later assessment of seroconversion (production of specific anti-SARS-CoV-2 antibodies). This will identify participants who had SARS-CoV-2 exposure and immunity prior to commencement of the study.
  - The baseline blood samples will be analysed in batch months after randomisation, so there will be no clinically actionable results. We will provide individualised results to participants via email after completion of the trial.
     This email will be sent to the applicable HRECs to review before being sent out to any participant.
  - o In Brazil, IGRA testing will be completed on pre-randomisation and 12-month blood samples as outlined in appendix 4.
- At 3 months and 6 months (+ 42 days) post randomisation, the study team will
  coordinate to collect study blood samples from participants and in a subset of
  participants at 9 and 12 months (+ 42 days) post randomisation. This will identify

- participants who had an immune response to SARS-CoV-2 (surrogate marker of infection) during the study. This is needed to determine asymptomatic SARS-CoV-2 infections.
- Blood samples will also be taken for assessment of the immune system. This will be
  used to meet the planned exploratory analyses related to vaccine induced changes in
  the immune system. These blood samples will be taken at the same time as blood
  collection for serum or plasma samples (i.e. at randomisation and post
  randomisation)
- In the eventuality that it is unfeasible to collect swab samples to confirm SARS-CoV-2 infection at the time of febrile or respiratory illness episodes (or conduct a validated RAT test), seroconversion may be used to associate episodes of febrile or respiratory illness with SARS-CoV-2 infection. Therefore, for episodes of febrile or respiratory illness where a swab sample cannot be taken, 1 month after the onset of symptoms (expected peak post-infection antibody production), participants may be asked to come to the hospital to provide a blood sample. If rapid point-of care testing is available, these tests may be distributed to participants to self-test. Should these alternative methods of testing become required, an amendment will be submitted to HRECs to outline the process and submit any information for participants. This testing will not be conducted without further consultation with and approval from the HRECs, including providing the HRECs with details of the test and its efficacy.

For blood sample collection for serum/plasma plus analysis of the immune system, a venous blood sample (up to 10ml or up to 35ml depending on the study site) will be taken by a trained member of the study team and labelled with participant ID, date/time collected, study timepoint, year of birth (no identifying information). Samples will be transported to the site's designated laboratory for the trial. Samples will be processed for serum/plasma separation and analysis of the immune system and stored at -80°C or in liquid nitrogen for later assessment.

A self-collected dried blood spot may be requested from participants instead of a venous blood sample collection. These may be stored in a locked cabinet prior to elution and storage at -80°C. If blood samples are done by participant self-collection of dried blood spot, participants will receive full instructions on how to take the samples, when to take them and how to correctly store them until they are returned to the study site.

#### Data Retrieval

Data retrieval is further described in Section 9 of this Protocol.

The present study expects that it will acquire some research data from existing administrative and service data sources. In Victoria, for example, this would include obtaining details from the Victorian Department of Health and Human Services (VDHHS) who collects information about presentations to hospitals and emergency departments for medical care in Victoria. Similar processes will be followed in other Australian states. In mainland Europe and Brazil, participants will be required to consent to provide access to their medical records by study staff. In the UK self—reports from participants may be supplemented by tracking of participants using their NHS number or other relevant unique identifiers (provided by

participant), drawing on Hospital Episode Statistics and Office of National Statistics data to track health service use (admissions) and deaths.

## 7.4 Notes on specific trial visits

#### 7.4.1 Unscheduled visit

If participants have any concerns related to side effects or the injection site evolution or scarring, they can call or email the study team for advice and if necessary, they will be seen by a clinician member of the study team or delegate. Reassurance, appropriate management or referral for medical care will be done according to best practice. Documentation of adverse event will be done as indicated in section 8.

## 7.5 Procedure discontinuation, participant withdrawals and losses to follow up

7.5.1 Discontinuation of blood collection - participant remains in trial for follow up Participants that decline further blood collection may still continue in all other aspects of the study.

7.5.2 Withdrawal of consent - participant withdraws from all trial participation Participants are free to withdraw from the trial at any time upon their request. Withdrawing from the trial will not affect their access to standard treatment or their employment as their participation will not be shared with their employer.

For the safety of all participants withdrawing from the trial, reasonable efforts should be made to undertake protocol-specified safety evaluations.

A dedicated Case Report Form (CRF) page will be used to capture the date of participant withdrawal of consent, and the reason if offered.

## 7.5.3 Losses to follow-up

Due to the study taking place with healthcare workers during a pandemic, we expect that there may be periods that participants will ignore the smartphone app prompts, phone calls or electronic messages. This includes the eventuality that a participant has been admitted to hospital. The weekly smartphone app prompts will only ask whether the participant has had a fever or respiratory symptom since the last time they answered in the app (date provided). Alternatively, where appropriate, phone follow-up will be used (i.e., Brazil). We deem this very unlikely to annoy participants excessively as they can ignore the notification or call if they are too busy (or withdraw). This will give the project the best chance of having a complete dataset to analyse as they can answer 'Yes' when they get the opportunity and fill in the associated questionnaire. Therefore, we will continue to send out weekly notifications or calls for the entire study regardless of whether participants respond.

In Australia and Europe, if a participant does not answer 2 regular smartphone app prompts (2 consecutive weeks), further attempts will be made to contact them by electronic messages (maximal 3 attempts), phone call (maximal 3 attempts) and email (maximal 3 attempts). If there is still no response, and the participant is not found to have died on medical records, we will try to contact them later (when the workload is expected to have decreased).

In Brazil, if a participant does not answer 3 follow-ups phone contacts (phone call or electronic messages), a home visit may be carried out by study staff. If there is still no response, and the participant is not found to have died on medical records, we will try to contact them later (when the workload is expected to have decreased).

Where secondary contact provided, the study team will follow-up if unable to contact participants.

#### 7.5.4 Replacements

Participants who have been randomised may NOT be replaced.

## 7.5.5 Trial Completion

A participant is considered to have completed the trial if he or she has completed all processes of the trial including the last visit or the last scheduled procedure shown in the Schedule of Assessments.

The end of the trial is defined as completion of the last visit or procedure shown in the Schedule of Assessments in the trial at all sites. At the end of the trial, the Sponsor-Investigator will ensure that all HRECs as well as all regulatory and funding bodies have been notified, if required.

This trial may be temporarily suspended or prematurely terminated if there is sufficient reasonable cause. If the trial is prematurely terminated or suspended, the Sponsor and Investigators will promptly inform trial participants, HRECs, the funding (where applicable) and regulatory bodies, providing the reason(s) for the termination or suspension.

Circumstances that may warrant termination or suspension include, but are not limited to:

- Determination of an unexpected, significant, or unacceptable risk to participants that meets the definition of a Significant Safety Issue (for the definition refer to Section 8.1).
- Insufficient compliance to protocol requirements
- Data that are not sufficiently complete and/or evaluable
- Demonstration of efficacy that would warrant stopping
- Determination that the primary endpoint has been met
- Determination of futility

In the case of concerns about safety, protocol compliance or data quality, the trial may resume once the concerns have been addressed to the satisfaction of the sponsor, HRECs, funding and/or regulatory bodies.

#### 7.5.6 Continuation of therapy

As the treatment is 'once-off' there is no provision for continuation of therapy.

#### 8 SAFETY MONITORING AND REPORTING

#### 8.1 Definitions

## Adverse Event (AE):

An AE is any untoward medical occurrence in a participant administered an investigational product and does not necessarily have a causal relationship with the study treatment. For this study, only certain adverse events are recorded, specifically serious adverse events as defined below, and non-serious adverse events of interest specified in section 8.2

#### Serious Adverse Event (SAE) :

Any serious adverse event (SAE) is an untoward medical occurrence that:

- Results in death; or
- Is life-threatening; or
- Requires hospitalisation or prolongation of existing hospitalisation;
  - o Hospitalisation is to be considered an SAE only in the event of an overnight admission. Any elective hospitalisation does not constitute an SAE
- Results in persistent or significant disability/incapacity; or
- Is a congenital anomaly/birth defect

Note: Life-threatening refers to an event in which the participant was at risk of death at the time of the event. It does not refer to an event that hypothetically might have caused death if it were more severe.

Medical and scientific judgement should be exercised in deciding whether an adverse event should be classified as serious in other situations. **Important medical events** that are not immediately life-threatening or do not result in death or hospitalisation but may jeopardise the participant or may require intervention to prevent one of the other outcomes listed in this definition should also be considered serious.

For this study, all SAE will be collected for the period from randomisation to 3 months post randomisation.

## Suspected Unexpected Serious Adverse Reaction (SUSAR):

A SUSAR is an AE that meets all of the following criteria:

- The AE is serious (as defined above; an SAE); and
- The SAE is suspected adverse reaction to the investigational product, meaning it is judged by either the reporting investigator or the Sponsor as having a reasonable possibility of a causal relationship to a study vaccine (possibly, probably or definitely related), and
- The SAE is also unexpected: An unexpected serious adverse reaction is one for which the nature or severity of the reaction is not consistent with reference safety information (Which is comprised of the BCG vaccine Product Information and the WHO information sheet: Observed rate of vaccine reactions Bacille Calmette Guerin Vaccine April 2012).

Note that an event is instead considered 'expected' if it is listed in the Reference Safety Information and therefore cannot meet the definition of SUSAR.

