#### **BCG** vaccination

Expected (common) reactions to BCG vaccination:

- A small swelling, redness and tenderness (measuring 0.5-1.5 cm in diameter) at the
  injection site appears within 1-2 weeks at the injection site. The local lesion evolves
  into a small ulcer. The ulcer heals over several weeks to months, usually healing into a
  small flat scar.
- Slightly swollen lymph nodes in the axilla in up to 10% of recipients, and usually resolve spontaneously.

Revaccination is associated with an earlier, accelerated reaction which begins within 24–48 hours of vaccination with induration followed by pustule formation in 5–7 days and healing within 10–15 days (https://www1.health.gov.au/internet/main/publishing.nsf/Content/cdacdi3701h.htm)

Tuberculous skin lesions are more common in people over 15 years or with revaccination).

Uncommon side effects of BCG vaccination (up to 1 in 100):

- Large ulcer, abscess at the injection site
- Keloid scar at injection site
- Swelling of lymph nodes in the armpit larger than 1 cm across

Rare side effects (up to 1 in 1000)

- Significant inflammation of lymph nodes in the axilla, sometimes with oozing ulcers, possibly abscess
- Infection with the bacteria from the vaccine can occur. The infection can spread throughout the body, including the bones (osteomyelitis)
- Allergic reaction or anaphylaxis (e.g.: redness of the face and neck, swelling of the face, throat or neck, skin rash, breathing difficulties and collapse)
- Fainting, seizures and convulsions (rare among patients receiving injections)

Very rare side effects (1–4 cases per million vaccinated people):

• Disseminated BCG infection has been reported rarely after BCG vaccination, mainly in immunocompromised individuals (who are excluded from the trial).

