## 8.6 Reporting of safety events

Site Principal Investigator Reporting Procedures:

The SPI (or delegate) is responsible for expedited reporting (within 24 hours of becoming aware of the event) to the Sponsor the following:

- •USMs
- •All SAEs (including SUSAR)

SAE reports should be submitted using the REDCap SAE form, or by alternative means specified in the Safety Reporting Plan.

At MCRI, the CPI (or delegate) will determine whether or not each SAE meets the definition of SUSAR and will notify all RPI in a timely manner.

The RPI and SPI will be notified of USM and other significant safety issues in a timely manner following MCRI first knowledge of the event/s.

In each country, USM, other significant safety issues, SUSARs and other SAE, will be reported to the applicable regulatory authorities and HRECs in accordance with the requirements.

Further details of event reporting responsibilities and processes are documented in the Safety Reporting Plan.

For safety reporting requirements specific to Brazil, refer to Appendix 4.

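### Protocol section 8.1 gives two conflicting tests of expectedness for a SUSAR, which disagree when a listed event is more severe than the reference safety information describes

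*Protocol*

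**What the plan says.** Section 8.1 sets three criteria for a SUSAR: the event is serious, it is suspected to be a reaction to the product, and it is unexpected. On the third it states: "An unexpected serious adverse reaction is one for which the nature or severity of the reaction is not consistent with reference safety information". It describes the RSI as "comprised of the BCG vaccine Product Information and the WHO information sheet" on BCG.

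The note that closes the definition says an event is instead "considered 'expected' if it is listed in the Reference Safety Information and therefore cannot meet the definition of SUSAR".

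Section 8.6 puts the definition to work. The chief principal investigator or delegate "will determine whether or not each SAE meets the definition of SUSAR and will notify all RPI in a timely manner", RPI being the regional principal investigators. Appendix 4 adds that in Brazil the regional investigator passes SUSARs on to the investigators of that region. Section 8.6 refers to a Safety Reporting Plan for reporting duties and procedures. It does not say that the plan defines expectedness.

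**The concern.** The third criterion tests two things, nature and severity. The note tests one, whether the event is listed. Severity is a separate attribute in this protocol: section 8.3 records it for each event and section 8.5 grades it from 1 to 5, with 5 fatal. A listed term therefore carries no particular severity by itself, and a person applying the note as written has no reason to look at severity.

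This matters because section 2.3.3 says BCG is used here outside its recommended use and that safety will be assessed in vaccine-naive and previously vaccinated workers. Section 2.3.1 already names several BCG complications as known, for example: "Disseminated BCG infection has been reported rarely after BCG vaccination, mainly in" immunocompromised people. Where complications are well known by name, greater severity than described is one of the main ways in which a new signal would show itself. A test based on listing alone would not treat it as unexpected.

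**Working it through.** No arithmetic applies to the conflict itself. The check sets the two rules side by side for a serious event judged at least possibly related.

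| Case | Third criterion | Closing note | Agree? |
|---|---|---|---|
| Not listed in the RSI, at any severity | Unexpected | Not triggered | Yes |
| Listed, nature and severity consistent with the RSI | Expected | Expected | Yes |
| Listed, severity greater than the RSI describes | Unexpected, so can be a SUSAR | Expected, so cannot be a SUSAR | **No** |

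The conflict is confined to the third row. The remaining safety text was then searched for anything that settles that row: the risk summary in section 2.3.1, the other definitions in 8.1, sections 8.2 to 8.6, and the Brazil safety reporting rules in Appendix 4. None restores the severity condition or says which sentence prevails.

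Next, what depends on the SUSAR label in that row:

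- Notification of all regional investigators by the chief principal investigator or delegate (section 8.6).
- In Brazil, onward notification of SUSARs to investigators in the region (Appendix 4).
- Any timelines that local requirements attach to SUSARs. Section 8.6 refers to those requirements without stating the timelines.

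What does not depend on it:

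- Sites report every SAE to the sponsor within 24 hours (section 8.6).
- SAEs that are not SUSARs are also reported to regulators and ethics committees as each country requires (section 8.6).
- A significant safety issue can be declared on seriousness and effect on benefit-risk, with no listing test (section 8.1). Regional and site investigators are then told (section 8.6).
- In Brazil, ethics committees hear of a causally related SAE within 7 days and a fatal one within 30 days, whether expected or not (Appendix 4).
- An independent safety monitor reviews SAE reports weekly, later monthly, then three-monthly (section 10.1.3).

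Last, timing. Section 1.3 expects dosing to end in March 2021, and section 8.1 collects SAEs for 3 months after randomisation. March 2021 plus 3 months is June 2021. Version 12.0 is dated 17 May 2022, more than ten months after the end of June 2021.

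**The case against.** The best defence is that the third criterion is the operative rule and the note only states its converse, so that listed should be taken to mean listed at that nature and severity. That reading would remove the conflict, and it is probably what a careful safety physician would do. But the note does not say it. It makes listing sufficient and draws an absolute consequence from it. The defence shows that the note can be repaired easily; it does not show that the text is consistent.

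Other parts of the defence stand and limit the point.

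- A reader might infer that a listed complication could never be a SUSAR. The documents do not support that. It follows only if the note governs, and the protocol gives the note no precedence. Its coming last and being more absolute is not a stated rule of construction.
- A reader might infer that grave BCG complications would escape detection or go unreported. They would not, given the routes listed above that do not depend on expectedness.
- A reader might take fatal or life-threatening disseminated BCG, osteomyelitis or suppurative lymphadenitis as proven examples. Each needs two facts about the RSI: that the term is listed, and that this severity is not described. Neither can be checked from the protocol. If the RSI describes the severity, both rules say expected and there is no conflict.
- The rate of 1 to 4 per million that section 2.3.1 gives for disseminated infection does not measure the problem. Neither rule tests frequency, and the rate is not that of a listed event at unlisted severity.

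The timing argument also stands: on the planned schedule, the 3-month SAE window had closed before this version, so much of the practical value lies in checking past decisions.

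**Conclusion.** The point holds as an internal contradiction in an operative definition. For a listed event of greater severity than the RSI describes, section 8.1 gives opposite classifications and nothing in the protocol resolves them. If the note is followed, the loss is the SUSAR classification and the notification that goes with it; the event is still reported as an SAE.

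The size is modest. The conflict covers one class of event, and the number of events in it cannot be estimated without the RSI and the SAE listings. No endpoint, analysis, power or alpha is affected. It is nevertheless worth correcting, because the definition is applied to every SAE and the correction is cheap.

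The conclusion that the two rules conflict rests on the text alone. Any statement about a named complication would rest on assumptions about the RSI, and the practical effect to date also depends on how the Safety Reporting Plan was applied, which is not shown.

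**What to change.** Delete the closing note in section 8.1, or reword it along these lines: an event is expected only if it is listed in the RSI and its nature and severity are consistent with that listing. This is what the third criterion already requires. A further test, such as one on outcome, is not needed to remove the conflict.

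Align the Safety Reporting Plan with the same wording. Then, since dosing and the 3-month SAE window were expected to have ended before version 12.0, review the SAEs judged possibly, probably or definitely related and confirm that none was classed as expected on listing alone.

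The cost is one sentence in the protocol, the matching text in the Safety Reporting Plan, and a short review of related SAEs. The downside is possibly a few more expedited reports.
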